### 3.0 Objectives

**Aim 1: Elucidate merits of transdiagnostic sampling.** Within the two intervention groups (Group 1: n = 24, Active iTBS and Active iTBS + APT; Group 2: n = 24, Placebo iTBS and Placebo iTBS + APT), we expect that (1i) neurologic diagnosis (stroke, TBI) will not moderate the effect of Active iTBS or Active iTBS + APT on Maximum Cognitive Gain as assessed by the Modified Digit Span (MDS) and the Streamlined AMPS (AMPS).

**Aim 2: Obtain pilot data to inform estimation of treatment and practice effects.** We will gather pilot data regarding the magnitude and duration of treatment effects as well as MDS and AMPS practice effects. As we anticipate (2i) greater immediate gains in IADL performance (AMPS) after Active iTBS + APT when compared to Active iTBS alone, we will compare Maximum Cognitive Gains (MCG) on MDS with MCG on AMPS between the Active iTBS and Active iTBS + APT groups to determine if MCGs differ in magnitude. We will also determine if

Active iTBS + APT trend lines indicate an additive treatment effect of APT on MDS and/or AMPS. We also anticipate (2ii) some persisting treatment effects and to explicate these effects we will examine effects for Active iTBS and Active iTBS + APT in the short-term (post-pre-treatment), long-term (2 weeks after a session) and cumulatively across treatment sessions. Since the AMPS uses a unique task during each testing interval and MDS uses 1 of 6 alternate test forms, we will determine (2iii) presence and magnitude of practice effects by testing whether prior exposure to MDS or AMPS results in MDS or AMPS gains for Placebo iTBS.

**Aim 3: Explicate study attrition by perceived suitability of aspects the study design and the relationship between this perceived suitability and fatigue as well as mood.** We will test the ideas that (3i) Attrition rates do not differ by stroke and TBI groups, (3ii) Veterans across stroke and TBI have similar perceptions regarding suitability of the number and type of tests as well as number of study-days, and (3iii) perceived suitability is related to Veteran-reported fatigue and mood.

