  - To optimize patient safety and mitigate risk, participant should be titrated off a specific medication(s) or receive a lower dose or alternate medication during study participation:
    - If clinical experts determine that the medication(s) can be safely withdrawn or changed, then participant remains eligible.
    - If clinical experts determine that the medication(s) cannot be safely withdrawn or changed, then the participant will be excluded.

To optimize patient safety and mitigate risk, participant should remain on medication as prescribed and remains eligible for study participation.

For Veterans remaining eligible, medical records will be further reviewed to document biological sex, age, time post ischemic stroke or TBI onset and current co-morbid medical conditions. Dictated radiology reports, as well as other records, will be reviewed to document right vs left cortical and sub cortical ischemic strokes and number of ischemic strokes. Radiology reports as well as clinical notes (e.g., History and Physical) will be reviewed to delineate TBI by etiology including diffuse axonal injury (DAI) and  $\geq 1$  contusion (e.g., blast, vehicular, assaults) or DAI +  $\geq 1$  contusion + an anoxic event subsequent to TBI (e.g., respiratory, cardiac). These variables will be examined for use as covariates in analyses.

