**Figure 1. Four Step Screening Process: Summary of Exclusion Criteria by Steps**

For this within-subject placebo-controlled partially-blinded treatment protocol (Fig 2), we will enroll 48 medically stable Veterans with stabilized recovery trajectories after a stroke or a TBI and who have a homogeneous level of moderately impaired cognitive function persisting after standard rehabilitation.

An equal number of Veterans with stroke/TBI (24-stroke; 24-TBI) will be enrolled, but we will over-sample females (Figure 2). For each iTBS group to include an equal number of Veterans with stroke/TBI, Veterans will be randomly assigned by diagnostic groups, to receive Active iTBS or Placebo iTBS. To measure immediate effects (ImE), an equal number of Veterans with stroke/TBI within each iTBS group will be randomly assigned to be tested with the Modified Digit Span (MDS) or AMPS, three times at 30 min intervals. Persisting effects (PE) tests will be administered to all participants at five timepoints including prior to and after Active iTBS or Placebo iTBS and 2-weeks later prior to the 2nd intervention, where all Veterans receive APT paired with their assigned iTBS (Active iTBS + APT or Placebo iTBS + APT). The alternate ImE test is then administered three times at 30 min intervals, followed by re-administration of all PE tests. Two weeks later, all PE tests are administered a 5th time (B4). ImE and PE measures are used to define magnitude and duration of cognitive change. Randomization (SAS Proc Plan) will be managed by one un-blinded researcher who will not provide interventions or conduct testing.

**Figure 2. Study Design (ImE = Immediate Effects Tests; AMPS = AMPS or MDS = Modified Digit Span; PE = Persisting Effects Tests for all participants; Study Day-1: Obtain Covariates and Treatment preparation information; B0 = Pre-Study-Day-2; B1 = Post-Study-Day-2; After 2-Weeks B2 = Pre-Study-Day-3; B3 = Post-Study-Day-3; After 2-Weeks B4 = Study-Day 4)**

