Average Placebo iTBS + APT MCG using t-tests for continuous data and z-tests for binary data. Using MLM, we will also determine if Active iTBS is related to more MDS or more AMPS gains. The group (Active iTBS or Placebo iTBS) by time interaction parameter will be used to examine if Active iTBS has a differential trend compared to Placebo iTBS. For 2i, we will also use MLM to identify presence of an additive effect of APT by examining Active iTBS + APT trend lines. For both the AMPS and the MDS outcomes, the group (Active iTBS + APT or Placebo iTBS + APT) by time interaction parameter will be used to examine if the Active iTBS + APT has a differential trend compared to Placebo iTBS + APT. For each intervention we will also determine (2ii) presence of persisting effects of Active iTBS and Active iTBS + APT in the short-term, long-term and cumulatively. Using the PE measures specified in Table 1 and t-tests, we will compare each PE measure for Active iTBS with Placebo iTBS and for Active iTBS + APT with Placebo iTBS + APT. Significant results will be reported. For (2iii), we will use one-tailed t-tests to identify presence of practice effects for MDS and AMPS. We will compare MDS and AMPS average peak gains after Placebo iTBS with average peak gains after Active iTBS. If the average Placebo iTBS peak gain is greater than the average Active iTBS peak gain for either MDS or AMPS, then we will repeat analyses above (for 2i and 2ii) using ImE and PE measures after adjusting them for the detected practice effects.

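### Aim 2ii compares the persisting-effects measures by unadjusted t-tests: B0 enters at most by subtraction, and diagnosis and ImE-test assignment are left out, so precision is lost

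*Combined protocol and SAP*

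**What the plan says.** Section 5.6 gives the whole Aim 2ii method in one sentence, "Using the PE measures specified in Table 1 and t-tests, we will compare each PE measure for Active iTBS with Placebo iTBS", and extends it to the paired sessions with APT. Mixed-effects models (MLM) are named for Aims 1i and 2i but not for 2ii.

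Three design facts in Section 5.1 bear on this:
- Baseline: "Persisting effects (PE) tests will be administered to all participants at five timepoints including prior to and after Active iTBS or Placebo iTBS". B0 is therefore taken before any iTBS.
- Stratum: "Veterans will be randomly assigned by diagnostic groups, to receive Active iTBS or Placebo iTBS".
- Second randomised factor: equal numbers by diagnosis "within each iTBS group will be randomly assigned to be tested with the Modified Digit Span (MDS) or AMPS", with the other test used at the second session.

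Section 3.0 describes the persisting effects as "in the short-term (post-pre-treatment), long-term (2 weeks after a session) and cumulatively across treatment sessions", and Section 5.1 adds that "ImE and PE measures are used to define magnitude and duration of cognitive change". No reference visit is given for the long-term or cumulative effect. The Table 1 that Section 5.6 cites for the PE measures is, in this document, the eligibility table.

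On covariates, the medical-records screening text says "These variables will be examined for use as covariates in analyses", which refers to variables from record review. Table 3 lists potential covariates to inform stratification in future research. Neither list is tied to Aim 2ii, and neither contains the B0 score or the ImE assignment.

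**The concern.** The design collects a baseline in every Veteran, randomises within diagnosis and randomises a second factor. The stated analysis is a two-sample comparison that models none of these.

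The ImE assignment could matter for some outcomes. At B1 and B3 the PE battery follows three MDS or three AMPS administrations, which Table 2 lists at 0.2 and 1.5 hours each. The battery itself contains WAIS-IV Digit Span and AMPS, so practice and fatigue may differ by assignment. The documents do not show how large this is.

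What is at stake is interval width and power. Aim 2 exists to supply effect-size estimates for a later trial, and 2ii tests many PE measures under false-discovery-rate control. Unused baseline information is therefore a direct cost to that aim.

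**Working it through.** **The plan's own figure.** For 0.90 SD at 80% power the plan states 21 per group. Assuming two-sided 0.05 (the sample-size text states neither alpha nor sidedness), the exact two-sample t calculation gives 21 per group, with power 81.2%. Attrition: 42 / (1 − 0.12) = 47.7, so 48. Both figures reproduce. For the plan's medium effect of 0.60 SD, the stated 42 per group gives 77.6% power; the t calculation needs 45.

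**Inputs.** n = 21 per arm and effects of 0.90 and 0.60 SD come from Section 5.6. The correlation ρ between B0 and a later PE score is not in the documents; it is assumed to be 0.5 to 0.8. The SD is taken as equal across visits.

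**Variance of the Active-minus-Placebo contrast, relative to a post-only score:**
- post-only: 1
- change from B0: 2(1 − ρ)
- B0-adjusted: 1 − ρ²

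The ratio of adjusted to change is (1 − ρ²) / [2(1 − ρ)] = (1 + ρ)/2.

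| ρ | change | adjusted | adjusted / change | adjusted / post-only |
|---|---|---|---|---|
| 0.5 | 1.00 | 0.75 | 75% | 75% |
| 0.6 | 0.80 | 0.64 | 80% | 64% |
| 0.7 | 0.60 | 0.51 | 85% | 51% |
| 0.8 | 0.40 | 0.36 | 90% | 36% |

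Against a change score, the standard error falls by 1 − √0.75 = 13% at ρ = 0.5 and by 1 − √0.90 = 5% at ρ = 0.8.

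**Power.** Noncentral t with noncentrality d√(n/2)/√V, where V is the relative variance above. Degrees of freedom are 2n − 2 = 40 for the t-tests and 2n − 5 = 37 for the adjusted analysis, which spends three on B0, diagnosis and ImE assignment but takes no credit for variance explained by the last two.

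| ρ | 0.90 SD, change | 0.90 SD, adjusted | 0.60 SD, change | 0.60 SD, adjusted |
|---|---|---|---|---|
| 0.5 | 81.2% | 90.6% | 47.5% | 59.0% |
| 0.6 | 88.9% | 94.4% | 56.4% | 65.8% |
| 0.7 | 95.7% | 97.8% | 68.8% | 75.5% |
| 0.8 | 99.4% | 99.7% | 85.1% | 88.4% |

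A post-only t-test has 81.2% and 47.5% at every ρ. If ρ were as low as 0.3, a change score would do worse than post-only (67.2% against 81.2% at 0.90 SD), while adjustment gives 84.5%.

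**Diagnosis and ImE assignment alone.** If together they explain 0% to 15% of the variance (assumed), adjusting for them without B0 moves power at 0.90 SD from 81.1% to 86.9%. Simulated type I error of the unadjusted t-test (24 per arm, 100,000 runs) is 0.051, 0.044, 0.038 and 0.028 when they explain 0%, 5%, 10% and 20%. The test is then conservative.

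**Session-2 increment.** With equal correlations between all visits, Cov(B0, B3 − B2) = ρ − ρ = 0. B0 then carries no information on B3 − B2, and adjusting for it gains nothing.

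**The case against.** The strongest reply is that the plan already uses B0. A reader might infer from the bare mention of t-tests that the baseline is ignored altogether. The documents do not support that: with the short-term effect defined as post minus pre and the PE measures said to define change, the session-1 effect reads as B1 minus B0. This stands. On that reading the post-only figures do not apply to the session-1 short-term effect, and a constant stroke–TBI difference cancels. A 0.5 SD diagnosis difference, for example, would add 0.5²/4 = about 6% to the variance of a post score but nothing to a change score.

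Second, at the effect the study was sized for, the gain over a change score is modest: 9.4 points at ρ = 0.5, falling to 0.3 at ρ = 0.8. This also stands. The gain is larger at 0.60 SD (11.5 falling to 3.3 points), an effect the plan does not claim to power.

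Third, diagnosis and ImE test are balanced within arm by design, every Veteran has had both ImE tests by B3, and Section 5.6 provides a conditional repeat of 2ii adjusted for practice effects. All true. Balance prevents bias, but it gives no precision unless the factors are in the model. The repeat is triggered only when the Placebo peak gain exceeds the Active one, and it is not an adjustment for assignment.

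Fourth, a linear mixed model may suit some PE ratings poorly, C-SSRS in particular. This is accepted and limits the fix.

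**Conclusion.** The point holds as a loss of efficiency. Aim 2ii as written makes no covariate adjustment for B0 and leaves out both randomisation factors. On either reading of its endpoint, adjustment gave higher power at every correlation tried from 0.3 to 0.8.

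A reader might go further and infer that the comparisons are biased or invalid. They are not: randomisation protects the t-test, which is at worst conservative.

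The size rests on an assumed correlation and on which endpoint is meant. For a change from B0, 10% to 25% of the variance is recoverable at correlations 0.8 to 0.5. For a post-only score it is 25% to 64% at correlations 0.5 to 0.8. The documents do not settle which applies to the long-term and cumulative effects. No gain should be claimed for the session-2 increment. Because Aim 2 feeds the design of a later trial and the data are already collected, the change is worth making even at the lower end.

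**What to change.** For the continuous cognitive and functional PE measures, replace the t-tests in Aim 2ii with one mixed model per measure over B0 to B4:
- B0 as baseline, either as a covariate by visit or constrained equal between arms;
- visit and arm-by-visit;
- diagnosis;
- ImE-test assignment by visit.

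Take the session-1 short-term, two-week and cumulative contrasts against B0. Report the session-2 increment (B3 versus B2) as a separate contrast from the same model, noting that B2 is measured after randomised treatment and that B0 adjustment is not expected to add precision there. State the reference visit for each effect, correct the Table 1 reference, and fix these covariates in advance. Measures that do not suit a linear model, such as C-SSRS, may keep a simpler comparison.

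The model also keeps the earlier visits of Veterans who drop out, in line with Section 5.7, which has data collected before withdrawal used in the analysis.

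Cost: SAP wording, slightly more programming and a few degrees of freedom. No new data are needed.

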## 5.6 Data Analysis

**Sample Size to Estimate Effect Sizes.** Our total sample size of 48 participants is based on 80% power to detect an Effect Size (ES) of .90. For 80% power, sample size per group to detect a small ES (0.35) is 130, for a medium ES (0.60) it is 42 and to detect a large ES (0.90) it is 21 per group. To estimate a large ES of 0.90, 42 subjects are required to achieve 80% power. Thus, we plan for 48 participants and 12% attrition.

Published methods  will be used to examine the merits of transdiagnostic sampling (Aim 1i). Specifically, we will use MLM to determine if neurologic diagnosis (stroke, TBI) moderates the effects of the Active intervention (Group 1: n = 24, Active iTBS and Active iTBS + APT; Group 2: n = 24, Placebo iTBS and Placebo iTBS + APT) on Maximum Cognitive Gain (MCG) as measured with the MDS and the AMPS.

For Aim 2, we will inform estimates of effect sizes by testing the idea (2i) that MDS gains and AMPS gains differ for Active iTBS and Active iTBS + APT. As specified in Table 1, we will examine if gains differ in magnitude by computing the MCGs for each outcome (MDS and AMPS) by each intervention. For each outcome, we will compare the Average Active iTBS MCG with the Average Placebo iTBS MCG and the Average Active iTBS + APT MCG with the

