For Aim 3, we will compute study attrition as percent of participants dropping out after Study-Day 2 and after Study-Day 3. We will examine whether or not these attrition rates differ (3i) by stroke and TBI groups using chi-square. To examine if Veteran's with stroke and TBI have (3ii) different perceptions regarding the suitability of the number and type of tests and number of study-days, we will compare each group's average ratings, by suitability index, using t-tests. To explore the relationship between perceived suitability and fatigue as well as mood (3iii), we will compute Pearson correlations at each of the 5-timepoints (B0 through B4) between average ratings of suitability indices 1 through 3 and averages for each of the two fatigue measures and each of the five mood measures [5x (3x2) + 5x (3x5) = 105 correlations]. We will also compute correlations for average suitability indices 7 through 8 collected on Study-Day 4 (B4) with the averages from that same day for each of the two fatigue measures and each of the five mood measures [1x (2x2) + 1x (2x5) = 14 correlations]. We will test the significance of each correlation using Fisher Z test and results will be interpreted accordingly.

Aims 2 and 3 involve multiple comparisons. Bonferroni correction of type I error rate is very conservative, and, at this early research stage, it could mask important findings. Thus, we will control for false discovery rate (FDR) using an FDR level of .05.

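### The only reporting commitment for persisting effects (2ii) covers significant results, so the reported effects would be selected and too large for an aim about magnitude and duration

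*Combined protocol and SAP*

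**What the plan says.** Section 3.0, Aim 2, sets out an estimation goal: "We will gather pilot data regarding the magnitude and duration of treatment effects". For 2ii, persisting effects are to be examined "short-term (post-pre-treatment), long-term (2 weeks after a session) and cumulatively across treatment sessions". Section 5.1 gives the measures the same role: "ImE and PE measures are used to define magnitude and duration of cognitive change".

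Section 5.6 then sets the 2ii analysis. Using t-tests, "we will compare each PE measure for Active iTBS with Placebo iTBS and for Active iTBS + APT with Placebo iTBS + APT". No covariate is named. The next sentence is the whole reporting plan for these comparisons: "Significant results will be reported". On multiplicity in Aims 2 and 3 it adds: "Thus, we will control for false discovery rate", at a level of .05.

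The sample size rests on a large effect: "To estimate a large ES of 0.90, 42 subjects are required to achieve 80% power". On allocation, section 5.1 says: "Veterans will be randomly assigned by diagnostic groups, to receive Active iTBS or Placebo iTBS". Diagnosis is therefore a randomisation stratum.

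**The concern.** An estimate that is shown only when it is significant is not an unbiased estimate. In a small trial the significance threshold lies far from zero, so a modest true effect can be reported only when chance has made it look large. The contrasts left out are the ones near zero, and those are what show that an effect has faded. A reader who sees only the significant contrasts would get effects that are too large and could not judge how long they last.

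The abstract says the findings will be used to develop a later study, so inflated values could carry forward. The filter is also specific to 2ii: for Aim 3 the same section tests every correlation and attaches no such condition.

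A separate and smaller matter is precision. The 2ii t-tests use neither the randomisation stratum nor the B0 score, although both are available.

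**Working it through.** **Inputs from section 5.6.** 24 per arm enrolled; 42 evaluable in total (21 per arm) after 12% attrition; effect sizes 0.35, 0.60 and 0.90 labelled small, medium and large; 80% power; FDR level .05.

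**Assumption.** Neither a per-test level nor sidedness is stated for 2ii. I use two-sided 0.05 because it broadly reproduces the plan's sample sizes.

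**1. Reproducing the plan's sample sizes.** Per group, n = 2(1.960 + 0.842)² / d² = 15.70 / d².
- d = 0.35: 128.2, so 129 (plan: 130)
- d = 0.60: 43.6, so 44 (plan: 42)
- d = 0.90: 19.4, so 20 (plan: 21)

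The exact t calculation gives 130, 45 and 21, so only the middle figure is slightly off. One-sided 0.05 gives 101, 35 and 16, which does not match. Attrition: 42 / 0.88 = 47.7, so 48.

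**2. Smallest observed effect that can be significant.** Threshold = t(0.975, 2n − 2) × √(2/n).
- 24 per arm: 2.013 × 0.2887 = 0.581
- 21 per arm: 2.021 × 0.3086 = 0.624

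**3. Average estimate among significant results.** Simulation of 400,000 two-arm trials per cell, two-sided p < 0.05:

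| True d | Power, 24/arm | Mean significant estimate, 24/arm | Ratio to truth, 24/arm | Ratio to truth, 21/arm |
|---|---|---|---|---|
| 0.20 | 10% | 0.67 | 3.4 | 3.5 |
| 0.30 | 17% | 0.74 | 2.5 | 2.6 |
| 0.35 | 22% | 0.76 | 2.2 | 2.3 |
| 0.50 | 40% | 0.80 | 1.6 | 1.7 |
| 0.60 | 53% | 0.84 | 1.4 | 1.5 |
| 0.90 | 86% | 0.99 | 1.1 | 1.1 |

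A separate run of 1,000,000 trials per cell agrees. At 0.35 it gives 2.17 (24 per arm) and 2.32 (21 per arm) on the standardised scale, and 2.09 and 2.21 on the raw mean difference. With no selection the standardised ratio is about 1.02.

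**4. Adding the planned FDR control.** The number of tests is not fixed in the text: section 5.6 points to Table 1 for the PE measures, but Table 1 holds the eligibility criteria and the battery is in Table 2. I assume 11 Table 2 rows × 2 interventions = 22 contrasts for one time horizon, or 22 × 3 = 66 for all three. I use Benjamini-Hochberg at 0.05, 24 per arm, the same true d in every contrast, and correlation between measures of 0 to 0.5.
- 22 contrasts: ratio 4.4 to 5.0 at d = 0.20, 2.5 to 2.8 at 0.35, 1.5 at 0.60, 1.1 at 0.90
- 66 contrasts: 4.4 to 5.4 at 0.20, 2.5 to 3.0 at 0.35

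If only a half or a quarter of the contrasts carry an effect of 0.35, the ratio reaches 3.2.

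**5. Covariates.** With correlation r between B0 and follow-up, a change-score comparison has variance proportional to 2(1 − r), and adjustment for B0 to 1 − r². The quotient is (1 + r)/2: 0.75, 0.85 and 0.90 at r = 0.5, 0.7 and 0.8. Simulated at 24 per arm with diagnosis in the model, it is 0.76, 0.87 and 0.92, so intervals are about 13%, 7% and 4% shorter. For B3 minus B2 with equal correlations between timepoints, B0 adjustment gives no gain (1.02). The documents give no value for r.

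**The case against.** **The sentence does not say only.** This stands as a matter of reading. The estimation language around it suggests loose drafting rather than an intention to suppress null results. But a team could omit every null contrast and still comply with this text. If full reporting is intended, saying so costs nothing.

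**The team keeps all the data.** Its own planning need not use filtered estimates, and a reader who knows the battery could infer that an omitted contrast was not significant. Both are fair. The reader would still lose the size and interval of each omitted contrast, and those are what magnitude and duration require.

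**The trial is sized for 0.90, where the ratio is 1.1.** Correct, and the ratio exceeds two only below about d = 0.4. However, section 5.5 says that immediate gains from a single session are unknown in TBI and stroke, and its large figure (g = .938) is for working memory in healthy controls. Nothing in the documents supports 0.90 for every PE measure, some of them taken two weeks after a session.

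**The 2.2 uses an unadjusted level, and the FDR figures rest on assumed families.** Also correct. But FDR control makes the filter stricter, so the unadjusted figure is the milder one.

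**Unadjusted t-tests are valid in a randomised pilot.** They are, so the covariate point is only about precision. It also presumes that the planned tests compare change scores, which the text does not say. The plan does list potential covariates (Table 3 and the medical-record screening text), but neither list names diagnosis or the B0 score as an adjustment.

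**Conclusion.** The concern holds. The one reporting rule for 2ii, taken as written, filters results by significance and conflicts with the stated purpose of Aim 2. At two-sided 0.05, the reported effects would average about 2.2 times the truth at an effect of 0.35 (2.3 at 21 per arm), 1.4 to 1.5 times at 0.60, and 1.1 times at 0.90. Under the planned FDR control the figure at 0.35 rises to about 2.5 to 3.0 if all contrasts share that effect.

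These sizes depend on the literal reading of the sentence, the assumed test level, the assumed FDR family and correlations, normally distributed measures, and a true effect that nobody yet knows. The direction of the bias does not depend on the particular values assumed. This should be changed before analysis. The covariate point is secondary and optional.

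**What to change.** **Main change.** In section 5.6, replace the reporting sentence for 2ii with:

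*All PE contrasts (short-term, long-term and cumulative) will be reported with the estimate, 95% confidence interval and FDR-adjusted p-value, whether or not significant.*

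Correct the table reference at the same point, so that the set of contrasts, and hence the FDR family, is fixed.

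**Optional.** For continuous PE measures, estimate the contrasts taken from B0 with the B0 score as a covariate and diagnosis as a factor, or use a mixed model over B0 to B4 with a common baseline mean. Choose a suitable alternative for measures that do not fit a linear model. The C-SSRS is one: section 5.1 has all participants answer only its first two questions.

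**Cost.** One sentence and a longer results table. The optional adjustment uses data already collected. No new visits or tests are needed.
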